APPENDIX 3.

Modified Rankin Scale (Sample)

Score	Description
0	No symptoms at all
1	No significant disability despite symptoms; able to carry out all usual duties and activities
2	Slight disability; unable to carry out all previous activities, but able to look after own affairs without assistance
3	Moderate disability; requiring some help, but able to walk without assistance
4	Moderately severe disability; unable to walk without assistance and unable to attend to own bodily needs without assistance
5	Severe disability; bedridden, incontinent and requiring constant nursing care and attention
6	Dead

## Revision History

Version #	Date (DD-Mmm-YYYY)	Document Owner	Revision Summary
V1.0	06-Mar-2020	██████████	Initial Release Version
V2.0	23-Mar-2021	██████████	Clarify determination of sample size Update analysis for secondary endpoints

[figure not shown]
This document is confidential.

## 1. Glossary of Abbreviations

Abbreviation	Description
AE	Adverse Event
AIS	Acute Ischemic Stroke
AUC	area under the concentration-time curve
AUC 0-t	AUC from time zero to the time of the last quantifiable concentration
AUC inf	AUC from time zero to infinity
ATC	Anatomical Therapeutic Chemical
CI	Confidence Interval
CL	Total Body Clearance (of Drug from Plasma)
C max	Maximum Plasma Concentration
CRF	Case Report Form
DSMB	Data Safety Monitoring Board
ECG	Electrocardiogram
ICF	Informed Consent Form
ITT	Intent-to-Treat
IV	Intravenous
IWRS	Interactive Web Response System
MedDRA	Medical Dictionary for Regulatory Activities
MRI	Magnetic Resonance Imaging
OR	Observational Research
mRS	Modified Rankin Scale
NIHSS	National Institute of Health Stroke Scale
PK	Pharmacokinetic
PP	Per-Protocol
PT	Preferred Term
QC	Quality Control
SAE	Serious Adverse Event
SAP	Statistical Analysis Plan
SD	Standard Deviation
sICH	Symptomatic Intracranial Hemorrhage

This document is confidential.

Abbreviation	Description
SOC	System Organ Class
SOP	Standard Operating Procedure
TEAE	Treatment Emergent Adverse Event
TFL	Tables, Figures, Listings
$t_{\max}$	time to reach $C_{\max}$
WHO	World Health Organization

This document is confidential.

## 2. Purpose

The purpose of this statistical analysis plan (SAP) is to ensure that the data listings, summary tables and figures which will be produced, and the statistical methodologies that will be used, are complete and appropriate to allow valid conclusions regarding the study objectives.

## 2.1. Responsibilities

## 2.2. Timings of Analyses

The primary analysis of safety, efficacy, and pharmacokinetics is planned after all subjects complete the final study visit or terminate early from the main phase of the study. Unless otherwise specified, the analysis includes all data collected in the database through the time of the database lock.

A series of ten horizontal black bars of varying heights, creating a stepped or staircase-like pattern. The bars are arranged vertically, with each subsequent bar being shorter than the one above it, starting from a full height at the top and ending with a small, nearly hidden bar at the bottom.

### 3. Study Objectives

#### 3.1. Primary Objective

To determine the safety of a single dose [REDACTED] of LT3001 drug product administered intravenously (IV) in subjects with acute ischemic stroke (AIS).

#### 3.2. Secondary Objective(s)

a) To determine the tolerability of a single dose [REDACTED] of LT3001 drug product administered IV in subjects with AIS.

b) To determine the potential efficacy of a single dose [REDACTED] of LT3001 drug product administered IV in subjects with AIS.

[REDACTED]

[REDACTED]

#### 3.3. Brief Description

This is a multicenter, double-blind, single-dose, randomized, and placebo-controlled prospective Phase IIa clinical study, designed to evaluate LT3001 drug product versus placebo/control in subjects with AIS.

There is only one dose of LT3001 drug product [REDACTED].

[REDACTED]

[REDACTED]

[REDACTED]

[REDACTED]

[REDACTED]

[REDACTED]

[REDACTED]

[REDACTED] Approximately 24 eligible subjects will be randomized 2:1 to LT3001 drug product or placebo. Each eligible subject will receive a single dose of LT3001 drug product or placebo within 24 hours after stroke symptoms onset. LT3001 drug product or placebo will be administered via a [REDACTED] IV infusion. The infusion will be stopped if an Serious Adverse Event (SAE) occurs during infusion.

The participation for each subject is approximately 92 days from the screening visit (Visit 1) to the last visit. The study design is illustrated in Figure 1.

[REDACTED]

This document is confidential.

### **3.4. Subject Selection**

#### **3.4.1. Inclusion Criteria**

Individuals must meet all of the following criteria to be included in the study:

1. Subject or subject's legal representative consented to participation by signing the informed consent form (ICF) after receiving full information about the study.
2. Subject is aged 18 to 90 years, inclusive, at the time of Screening [REDACTED].
3. Subject has a NIHSS of 4 to 30.
4. Subject has a clinical diagnosis of AIS within 24 hours after stroke symptoms onset.  
[REDACTED]  
[REDACTED]
5. [REDACTED]
6. Subject is able to receive the investigational product (IP) within 24 hours after stroke symptoms onset.
7. Subjects are women of childbearing potential (WOCBP) or men whose sexual partners are WOCBP, are able and willing to use at least 1 highly effective method of contraception during the study until 3 months after dosing of IP.

#### **3.4.2. Exclusion Criteria**

Individuals meeting any of the following criteria at Screening [REDACTED] or Baseline are ineligible to participate in this study:

1. Subject has been treated with rtPA and/or endovascular thrombectomy (EVT) during the current AIS.
2. Subject has a pre-stroke disability that requires help for activities of daily living [REDACTED].
3. Subject has imaging evidence of acute intracranial hemorrhage, intraparenchymal tumor, arteriovenous malformations, other central nervous system lesions that could increase the risk of bleeding, or aneurysm requiring treatment.
4. [REDACTED]  
[REDACTED]
5. Subject has symptoms of suspected subarachnoid hemorrhage [REDACTED].
6. Subject has generalized seizure [REDACTED].
7. Subject has current uncontrolled hypertension [REDACTED].
8. Subject has International Normalized Ratio (INR) >1.7, abnormal activated partial thromboplastin time (aPTT) or platelet count <100,000/mm^3.
9. Subject has blood glucose concentration <50 mg/dL or >400 mg/dL.

This document is confidential.

10. Subject is lactating, pregnant (pregnancy test required for all female subjects), or planning to become pregnant during the study.
11. Subject has received anticoagulants within 48 hours prior to treatment, e.g., direct oral anticoagulants (e.g., dabigatran, rivaroxaban, apixaban, edoxaban), low molecular weight heparin (e.g., enoxaparin), fondaparinux.
12. Subject has received oral dual antiplatelet therapy and glycoprotein (GP) IIb/IIIa inhibitors within 48 hours prior to treatment.
13. Subject has had prior AIS, myocardial infarction, or serious head trauma within 90 days of Screening [REDACTED].
14. Subject has history of ICH within 90 days of Screening [REDACTED].
15. Subject has had any major surgery within 90 days of Screening [REDACTED], e.g., intracranial or intraspinal surgery, coronary artery bypass graft, obstetrical delivery, organ biopsy.
16. Subject with bleeding event within 21 days of Screening [REDACTED], e.g., gastrointestinal or hemorrhage.
17. Subject has puncture of noncompressible vessels within 7 days of Screening [REDACTED].
18. Subject has severe hepatic, renal, and/or active infectious disease at Screening [REDACTED].
19. Subject has participated in another investigational study and received IP within 30 days of Screening [REDACTED] or 5 half-lives (whichever is longer).
20. In the opinion of the Investigator, the subject is not appropriate for the study for any other reason.

### **3.5. Determination of Sample Size**

Approximately 24 eligible subjects will be randomized 2:1 to LT3001 drug product or placebo. It is planned to have 24 subjects randomized, after which enrollment will stop.

### **3.6. Treatment Assignment & Blinding**

The study is placebo-controlled to lessen the risk that events due to chance are falsely attributed to LT3001 drug product.

The study is randomized to control for factors known and unknown between the treatment groups.

The study is blinded so that the subjects, site staff administering the study treatment (LT3001 drug product or placebo), and site staff conducting study assessments will not know which treatment a subject receives to allow assessment of the study objectives without bias.

Subjects will be randomly assigned to receive LT3001 drug product or placebo in a ratio of 2:1.

At Screening [REDACTED] the Subject Number. This number will be associated with the subject throughout the study. [REDACTED]  
[REDACTED]

This document is confidential.

[REDACTED]  
[REDACTED]  
[REDACTED]  
The subjects will be centrally randomized at a study level. The treatment assignment will be determined by a randomization list prepared by the biostatistics group [REDACTED]

[REDACTED].  
According to the randomization schedule as indicated in the Schedule of Assessments and in accordance with the pharmacy manual, [REDACTED] the Investigator or designee at the study site will be responsible to provide the Subject Number, [REDACTED] to the unblinded pharmacist or designee for the calculation of study treatment dosage. The unblinded pharmacist or designee will further confirm the Subject Number, [REDACTED] and the study treatment [REDACTED] [REDACTED] and the dosage calculation, after which he/she will prepare the study treatment. Prepared study treatments will be identical in appearance and labeled in a blinded manner. Information included on the label includes the Protocol Number, Subject Number, Randomization Number, etc. No other study site personnel, subjects, Sponsor personnel, or Sponsor designees will be unblinded to treatment assignment throughout the duration of the study unless unblinding is required. If an Investigator becomes unblinded to a given subject's study treatment, that subject will be discontinued from the study unless there are ethical reasons for that subject not to be discontinued; approval from the Medical Monitor must be obtained in such instances.

[figure not shown]
The Investigator must make every effort to contact the Medical Monitor prior to unblinding a subject. In the rare event that contact with the Medical Monitor is not possible prior to unblinding, the Investigator reserves the right to unblind in a true emergency, where subject safety is at immediate risk. The unblinding and its cause will also be documented in the electronic Case Report Form (eCRF) [REDACTED]  
[REDACTED].

### 3.7. Administration of Study Medication

Subjects randomized to LT3001 drug product will receive a single dose of LT3001 drug product [REDACTED] [REDACTED] administered as a [REDACTED] IV infusion. Subjects randomized to placebo will receive placebo as a [REDACTED] IV infusion as well.

This document is confidential.

**3.8. Study Procedures and Flowchart**

[figure not shown]

This document is confidential.

**Statistical Analysis Plan**

Sponsor: Lumosa Therapeutics Co, Ltd; Protocol No.: LT3001-201

---

This document is confidential.

SAP Version: 2.0, 23-Mar-2021

Filing requirements: TMF

Page 16 of 47

## **4. Endpoints**

### **4.1. Primary Endpoint**

[figure not shown]
The primary endpoint of this study is the occurrence of symptomatic intracranial hemorrhage (sICH) within 36 hours after dosing -- clinical deterioration defined as an increase in the National Institute of Health Stroke Scale (NIHSS) of 4 points or more AND confirmed by computed tomography (CT)- or magnetic resonance imaging (MRI)- documented.

### **4.2. Secondary Endpoints**

The secondary efficacy and safety endpoints are as follows:

- The occurrence of sICH [REDACTED].
- The occurrence of asymptomatic intracranial hemorrhage (ICH) [REDACTED]  
[REDACTED].
- The occurrence of mortality due to intracerebral or other major bleeding complications [REDACTED]  
[REDACTED].
- The occurrence of mortality due to any reason [REDACTED].
- The number and severity of AEs [REDACTED].
- The number of subjects with AEs [REDACTED].
- The occurrence of recurrent stroke [REDACTED].
- Functional outcome
  - The frequency and percentage of subjects with each grade on modified Rankin Scale (mRS) [REDACTED]  
[REDACTED].
  - The frequency and percentage of subjects with mRS  $\leq 2$  [REDACTED].
- Neurological outcome
  - Absolute change in NIHSS [REDACTED].
  - The proportion of subjects with NIHSS  $\leq 2$  [REDACTED].

[REDACTED]

This document is confidential.

## **5. Analysis Sets**

### **5.1. Enrolled Population**

The Enrolled Population will include all individuals who sign the ICF. Unless specified otherwise, this population will be used for subject listings and for summaries of subject disposition.

### **5.2. Safety Population**

The Safety Population will include all randomized subjects who receive at least 1 dose of IP. The treatment group assignment in this population will be defined by the treatment actually received. This population will be used for the analysis of safety.

### **5.3. Intent-to-Treat (ITT) Population**

The ITT population will include all subjects who are randomized, irrespective of any deviation from the protocol or premature discontinuation. The treatment group assignment will be designated according to initial randomization. The ITT population will serve as the primary basis for the analysis of efficacy.

### **5.4.**

### **5.5. Per-Protocol (PP) Population**

The PP population will comprise all ITT subjects who complete study procedures through Day 90 without a major protocol deviation potentially impacting efficacy measurements. The PP population will also be used for the analysis of efficacy.

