7.3 End of Study

A subject will have fulfilled the requirements for study completion when the subject has completed all study periods, including the last scheduled follow-up visit as indicated in the Schedule of Assessments ([Table 10-1](#)).

The end of the study will be the last subject's last visit.

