14.2 Analysis Populations

Enrolled Population

The enrolled population will include all individuals who sign the ICF.

Intent-to-Treat (ITT) Population

The ITT population will include all subjects who are randomized, irrespective of any deviation from the protocol or premature discontinuation. The treatment group assignment will be designated according to initial randomization. The ITT population will serve as the primary basis for the analysis of efficacy.

Per-Protocol (PP) Population

The PP population will comprise all ITT subjects who complete study procedures through Day 90 without a major protocol deviation. The PP population will also be used for the analysis of efficacy.

Safety Population

The safety population will include all randomized subjects who receive at least 1 dose of investigational product. The treatment group assignment in this population will be defined by the treatment actually received. This population will be used for the analysis of safety.

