## 7. Demographic, Other Baseline Characteristics and Medication

### 7.1. Subject Disposition and Withdrawals

Subject disposition will be summarized and listed.

The number and percentage of subjects in each population, completed and discontinued the study, together with the reasons for discontinuation (unacceptable toxicity or AE, subject withdrawal of consent, intercurrent illness, general or specific changes in the subject's condition, subject fails to adhere to the protocol requirements, lost to follow-up, pregnancy, study terminated, other) will be presented.

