## **8. Efficacy**

Efficacy analyses will be conducted for the ITT population, evaluable population PP population and safety population. All statistical tests for secondary efficacy endpoints will be two-sided with  $\alpha = 0.05$ .

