### **8.1. Primary Efficacy Endpoint and Analysis**

There will be no primary efficacy endpoint or analysis carried out for this study.

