#### **8.2.3. National Institute of Health Stroke Scale**

The NIHSS is a standardized method to measure the level of impairment caused by a stroke and was developed by the National Institutes of Health. The NIHSS allows for objective comparison of efficacy across different treatments for stroke, including rehabilitation interventions.

The NIHSS is a brief and reliable stroke deficit assessment scale composed of 11 components and the numbers of grades for each component vary; however, for each component, a score of 0 is defined as normal while higher scores indicate increasing severity of impairment. The total score ranges from 0 (no deficit) to 42 (dead).

[REDACTED]  
[REDACTED]

The total score and absolute change from baseline will be summarized [REDACTED]. Data missing on the visit level will not be imputed, and no statistical inferences will be performed.

The proportion of subjects with NIHSS of 0-2 points will be presented by treatment group [REDACTED]

[REDACTED]  
[REDACTED]

This document is confidential.

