## 10.5. Vital Signs

Vital signs includes body temperature (°C), pulse rate (beats/min), respiration rate (breaths rate/min), systolic and diastolic blood pressure (mmHg). Body temperature (°C) and respiration rate (breaths rate/min) will be collected [REDACTED]

[REDACTED]. Pulse rate (beats/min) and systolic and diastolic blood pressure (mmHg) will be collected at Screening (Visit 1), Visit 2 (Day 0), Visit 2-PK (5 min, 10 min, 15 min, 30 min and 1 hours after dosing), Visit 3 (24 Hours), on Visit 4 (Day 7), Visit 5 (Day 30) and at ET.

Vital signs will be summarized at each time point by treatment, using mean values and mean change from baseline values, as well as numbers of subjects with values outside limits of the normal range. Shift table (normal, abnormal NCS, abnormal CS) will also be provided at each time point by treatment.

Subject listing of vital signs will be provided. Subjects with abnormal vital signs interpretation will be presented in the listings.

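### The SAP 5.5 per-protocol rule requires Day 90 completion, so patients who die earlier leave PP regardless of adherence: a minor defect in a supportive analysis set

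*SAP*

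**What the plan says.** SAP 5.5 defines PP as "all ITT subjects who complete study procedures through Day 90 without a major protocol deviation potentially impacting efficacy measurements", and says that PP will also be used for efficacy. Protocol 14.2 has the same Day 90 condition: "The PP population will comprise all ITT subjects who complete study procedures through Day 90 without a major protocol deviation". SAP 12 records that the definition was revised, but the visible revision narrows only the deviation wording and leaves the completion condition in place.

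Protocol 7.3 treats study completion as reached when "the subject has completed all study periods, including the last scheduled follow-up visit". SAP 7.1 will report "The number and percentage of subjects in each population, completed and discontinued the study", with reasons for discontinuation. Those reasons include toxicity or adverse event, and other; death is not listed separately.

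On the role of PP, SAP 8 states: "Efficacy analyses will be conducted for the ITT population, evaluable population PP population and safety population". SAP 5.3 makes ITT, which keeps every randomized subject, the primary basis for efficacy. SAP 8.1 adds: "There will be no primary efficacy endpoint or analysis carried out for this study". SAP 8.2.4 describes the mRS as a scale from 0 to 6 on which 6 is death, and SAP 8.2.3 puts death at the top of the NIHSS range, at 42.

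**The concern.** A per-protocol set is meant to show results in patients who followed the protocol. The second half of the SAP 5.5 rule does that, by removing deviations that could affect efficacy measurements. The first half removes anyone who does not reach Day 90, and death is one way not to reach it. Membership then depends partly on an outcome that occurs after randomization and that the mRS itself grades.

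At stake is how PP reads beside ITT. If the two disagree, the natural explanation is non-adherence, but the disagreement could come entirely from deaths among fully adherent patients. If deaths are unequal between arms, the arm with more deaths tends to look better in PP. Protocol 5.4 says that efficacy outcomes from this study will guide later studies, and a responder rate among survivors would be a poor planning input.

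**Working it through.** **Reading the rule.**

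1. PP requires completion of procedures through Day 90 (SAP 5.5, Protocol 14.2).
2. Completion includes the last scheduled follow-up visit (Protocol 7.3). A patient who dies earlier cannot attend it, and no visible text counts death as completion.
3. Every death before Day 90 is therefore outside PP, and the PP Day 90 count of mRS 6 from such deaths is zero by construction.
4. Membership is fixed per patient, not per visit, so the patient's earlier scores go too. SAP 10.5 names visits at 24 hours, Day 7 and Day 30 for vital signs; the efficacy schedule is not visible.
5. A redacted scoring rule could assign a value to a death, but it would not readmit a patient whom SAP 5.5 excludes.

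**Inputs for the size.** From the documents: about 24 randomized 2:1 (SAP 3.5), so 24 × 2/3 = 16 on LT3001 and 24 × 1/3 = 8 on placebo. The documents give no mortality or responder rate to reproduce. Assumed: mRS 0-2 in 50% of each arm (8/16 and 4/8), deaths only among non-responders, no other PP exclusions.

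**Chance of at least one death.** 1 − (1 − m)^24 is 71%, 92% and 98% for assumed mortality m of 5%, 10% and 15%.

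**Individual deaths.** The PP rate is responders ÷ (arm size − deaths).

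| Deaths | PP rate | Change from 50% |
|---|---|---|
| 1 on LT3001 | 8/15 = 53.3% | +3.3 points |
| 1 on placebo | 4/7 = 57.1% | +7.1 points |
| 2 on placebo | 4/6 = 66.7% | +16.7 points |

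At an assumed responder rate of 25%, one death adds 4/15 − 4/16 = 1.7 points (LT3001) or 2/7 − 2/8 = 3.6 points (placebo). At 75% it adds 12/15 − 12/16 = 5.0 or 6/7 − 6/8 = 10.7 points.

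**Mean effect over random deaths.** Let D1 ~ Bin(8, 2m1) and D0 ~ Bin(4, 2m0). The factor 2 places arm-level mortality m on the non-responding half of the arm. The mean inflation is E[8/(16 − D1)] − 0.5 on LT3001 and E[4/(8 − D0)] − 0.5 on placebo.

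| Mortality, LT3001 / placebo | Inflation, LT3001 | Inflation, placebo | Between-arm distortion |
|---|---|---|---|
| 5% / 5% | +2.8 | +3.0 | −0.2 |
| 10% / 10% | +5.9 | +6.3 | −0.4 |
| 15% / 15% | +9.4 | +10.0 | −0.6 |
| 15% / 5% | +9.4 | +3.0 | +6.4 |
| 5% / 15% | +2.8 | +10.0 | −7.2 |

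Figures are percentage points; a positive distortion favours LT3001. Equal mortality raises both arms alike and almost cancels. A directional distortion needs unequal deaths, and it then favours the arm with more of them.

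**Yardstick.** The standard error of the ITT difference at 50% is √(0.25/16 + 0.25/8) = 0.2165, or 21.7 points.

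**The case against.** The strongest case on the other side is that this hardly matters. ITT is primary for efficacy and keeps all randomized patients, and there is no primary efficacy endpoint. Equal mortality distorts the difference by less than one point, and the larger figures need an assumed threefold mortality imbalance with every death among non-responders. All of this stands, and it sets the weight of the point.

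A reader might infer that deaths are hidden, or that adherence and survival cannot be told apart. The documents do not support either. Mortality is reported by treatment group (SAP 10.12 and 10.13), population counts and reasons for discontinuation are tabulated (SAP 7.1), and all data are listed (SAP 6.1). With about 24 patients, a reader can largely work out who left PP through death.

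A reader might also infer that no supportive set keeps deaths. That cannot be said: SAP 8 names an evaluable population whose definition is not visible, and it may retain them. Nor can it be said that the plan lacks a scoring rule for deaths, because parts of SAP 8.2.3, 8.2.4 and 12 are redacted.

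Finally, mean NIHSS change is not a problem special to PP. SAP 6.3 rules out imputation, so at visits after a death any population without a score for death describes survivors only, ITT included. The point is therefore confined to PP membership, the PP mRS results and the PP responder proportions.

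**Conclusion.** The point holds as a minor defect. On the readable text, every death before Day 90 leaves PP whatever the patient's adherence, and no redacted scoring rule could reverse that. PP and ITT can therefore differ solely because patients died.

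Under the stated assumptions, one death moves the PP responder rate by 3.3 points on LT3001 or 7.1 on placebo. The mean between-arm distortion is −0.2 to −0.6 points at equal mortality of 5% to 15%. With a 15% versus 5% imbalance, the arm with more deaths gains 6.4 points if it is LT3001 and 7.2 if it is placebo. All of this is small beside a standard error of 21.7 points, and the rates are illustrative because the documents give none.

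It would go too far to say that PP is biased in favour of LT3001: the direction depends on which arm has more deaths, which the documents cannot tell. Nor do the ITT membership rule, the sICH analysis or the mortality analyses depend on the PP definition.

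**What to change.** 1. In SAP 5.5, insert the words *or die before Day 90* after the Day 90 completion condition, keep the deviation clause as it is, and list the change in SAP 12.
2. Unless a redacted rule already does so, state that these deaths enter the PP mRS tables as mRS 6 at scheduled visits after death, and count as not achieving mRS 0-2 or NIHSS 0-2. Leave the NIHSS component of the sICH definition and SAP 10.14 unchanged.
3. Under mean NIHSS change, footnote the number of deaths by arm, because that summary stays survivor-only at visits after death wherever death has no score.

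The cost is one clause, one sentence, one footnote and one line in SAP 12. No new data are needed, since mortality is already an endpoint. There are three downsides. PP will include patients without a Day 90 visit. PP responder rates become slightly less favourable. Living patients who leave early stay excluded, so any outcome-related selection among them remains.
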